5. ASSESSMENT OF SAFETY

The events reported during the entire course of the study for patients will be evaluated. The data will be examined for the types of events reported and their frequency of occurrence. Re-operations, revisions, removals or supplemental fixation will be assessed at each post-surgical follow-up visit.

5.1 Adverse Events

An Adverse Event (AE) is any untoward medical occurrence in a clinical study patient. All AEs will be recorded in this study. An AE can be any unfavorable and unintended sign, symptom, or disease regardless of the relationship to the product.

5.2 Recording and Reporting Adverse Events

For the purpose of AE recording, the study period is defined as the time period from surgery through discharge from the hospital. All AEs will be reported to 7D Surgical. Any reported AE that occurs after the study follow-up period (regardless of time after study participation) will be assessed for its relationship to the patient's participation in the study. If an AE occurs after the study follow-up period and is considered by the investigator to be possibly related to study participation, it must be recorded and reported.

5.3 Relationship to the Imaging System

The investigator will evaluate the relationship of the AE to the MvIGS spine navigation system according to the following definitions:

- Definite** The AE is clearly related to the spine navigation system: the event has a temporal relationship, and no alternative cause is present.
- Probable** The AE is likely related to the spine navigation system: the event has a temporal relationship, follows a known or suspected pattern of response, or is otherwise logically related, but an alternative cause may be present.
- Not Related** The AE is clearly not related to the spine navigation system: the event has no temporal or other relationship to the use of navigation, follows no known or suspected pattern of response, and an alternative cause is present.
- Unknown** Unable to determine the relationship based on all available information.

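### Section 5.3 bars any adverse event with a time link to navigation from being rated Not Related, even when another cause is clear

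*Combined protocol and SAP*

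**What the plan says.** Section 5.3 is prescriptive: "The investigator will evaluate the relationship of the AE to the MvIGS spine navigation system according to the following definitions". Four levels follow, each made of a general judgement and then a list of conditions.

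- *Definite*: "the event has a temporal relationship, and no alternative cause is present".
- *Probable*: one that "has a temporal relationship, follows a known or suspected pattern of response, or is otherwise logically related, but an alternative cause may be present"; the list is joined by 'or'.
- *Not Related*: "the event has no temporal or other relationship to the use of navigation", and in addition the event "follows no known or suspected pattern of response, and an alternative cause is present".
- *Unknown* (the fallback): "Unable to determine the relationship based on all available information".

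Section 5.2 sets the recording period as surgery to hospital discharge and sends every adverse event in that period to the sponsor. It treats events after that period separately. If such an event is "considered by the investigator to be possibly related to study participation, it must be recorded and reported".

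**The concern.** The conditions for *Not Related* are cumulative, and the first is the absence of any time link to navigation. In the MvIGS arm navigation is used during the operation that opens the recording period. An event in the operating room or on the first days of the stay can therefore be close in time to navigation and still have an obvious cause elsewhere. An anaesthetic reaction is an illustration (the example is mine, not the protocol's). An investigator who follows the text cannot call it unrelated.

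The 5.3 rating is the only place where the protocol grades whether MvIGS contributed to harm, and Section 9 foresees sponsor reports from these data to regulatory authorities. Events labelled *Probable* on timing alone overstate device harm. Events labelled *Unknown* when the cause is known hide information that the site has. An investigator who sets the text aside in order to rate sensibly will produce ratings that differ between raters.

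**Working it through.** The protocol gives no figure on this point, so there is nothing to reproduce. The check is one of logic.

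**Attributes, all from Section 5.3.** T = temporal relationship to navigation; P = known or suspected pattern; L = other logical link; A = alternative cause present. Each is yes (1) or no (0), which gives 2 × 2 × 2 × 2 = 16 combinations.

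**Conditions as written, and how many combinations meet each:**

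| Level | Condition | Combinations |
|---|---|---|
| *Definite* | T = 1, A = 0 | 2 × 2 = 4 |
| *Probable*, 'or' read literally | at least one of T, P, L | 16 − 2 = 14 |
| *Probable*, strict reading | T = 1 and at least one of P, L | 3 × 2 = 6 |
| *Not Related* | T = 0, P = 0, L = 0, A = 1 | 1 |

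Eight combinations have T = 1. None of them meets *Not Related*.

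**The case at issue: T = 1, P = 0, L = 0, A = 1.**

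1. *Not Related* fails because T = 1.
2. *Definite* fails because A = 1.
3. *Probable*, read literally, is met on T alone.
4. *Probable*, read strictly, fails because P and L are both 0. No substantive level is left, only *Unknown*, whose own definition (relationship cannot be determined) does not describe an event with a known cause.

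The fourth attribute matters. If L = 1, the event is *Probable* on both readings, and that result is unremarkable. The defect is confined to events where timing is the only connection to navigation. It is also confined to the MvIGS arm, since the fluoroscopy arm has no use of navigation to which an event could be linked in time.

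**What uses the rating.** Section 2.2 counts reported complications in hospital. Section 4.2 compares complication rates between arms by chi-square or Fisher's exact test. The opening of Section 5 examines types and frequencies of events. Section 5.1 records all events regardless of relationship, and Section 5.2 reports all in-period events to the sponsor. None of these depends on the 5.3 level.

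**The same check on reworded definitions.** Let *Not Related* be P = 0, L = 0, A = 1 with T free: 2 combinations, now including the case at issue. Let *Probable* be T = 1 with P or L: 6 combinations. The two cannot overlap, because one needs P = L = 0 and the other needs P or L. *Definite* stays at 4, of which 3 also meet *Probable*, so 4 + 6 − 3 + 2 = 9 combinations have a substantive level. The other 16 − 9 = 7 go to *Unknown*: the 3 × 2 = 6 with a pattern or logical link but no time link, and the 1 with none of the four attributes.

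**The case against.** The strongest reply is that each level opens with an overall judgement (clearly related, likely related, clearly not related) and that the listed conditions only illustrate it. An anaesthetic reaction is not likely to be related to navigation, so a sensible investigator would not choose *Probable*. This softens the problem but does not remove it. Section 5.3 tells the investigator to rate by the definitions, and the text after the opening judgement still rules out *Not Related* for any event with a time link.

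A second reply is that the protocol does not define a temporal relationship to the use of navigation. Urinary retention on day 1 could be read as having none. That is fair, and it is why no share of affected events can be stated. It also leaves the rating dependent on each rater's private reading.

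A third reply is that no planned table or test uses the rating. That stands in full, and it limits the consequence to device attribution.

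A reader might also infer that Sections 5.2 and 5.3 contradict each other, because 5.2 turns on an event being possibly related while 5.3 has no such level, and that late device events could therefore go unrecorded. The documents do not support this. Section 5.2 asks about relationship to study participation, in either arm. Section 5.3 rates relationship to the navigation system. Section 5.2 does not refer to the 5.3 scale, and it already requires any late event judged possibly related to be recorded and reported. A 5.3 rating of *Unknown* does not prevent that judgement. The threshold is undefined, but it is neither contradicted nor missing a route. Nothing in the documents requires a scale to have a *Possible* level.

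**Conclusion.** The definition of *Not Related* is faulty as written. A perioperative MvIGS-arm event with a time link, no pattern or logical link, and a clear other cause cannot meet it, and falls to *Probable* or *Unknown* depending on how one 'or' is read. The conclusion rests on two assumptions: that the listed conditions are applied as definitions, and that at least some in-hospital events count as linked in time to navigation.

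The effect is limited to the graded device attribution. The primary analysis, the sample size, the between-arm complication comparison and the reporting of in-period events are untouched. How many events would be misrated cannot be determined from the documents. A reader might go further and infer that a planned table of device-related events would be wrong, or that a real navigation signal would be buried. No such table is planned, and every event is recorded and reported whatever its rating, so that inference goes beyond the text. The point deserves a correction because the wording misdirects the rater and costs almost nothing to repair.

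**What to change.** In Section 5.3:

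- Reword *Not Related* so that an event clearly explained by another cause, with no known or suspected pattern and no other logical link to navigation, qualifies whatever its timing.
- Reword *Probable* to require a temporal relationship and, in addition, either a known or suspected pattern or another logical link, so that timing alone is not enough.

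In Section 5.2, keep the late-event trigger as it is, for both arms. Do not replace it with the 5.3 device ratings: a late event related to study participation but not to MvIGS, including any in the fluoroscopy arm, could then drop out of mandatory reporting. At most, add a sentence that a 5.3 rating of *Unknown* does not exempt a late event from reporting. A *Possible* level is optional. If one is added, its conditions must not overlap with those of *Probable*.

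The cost is the rewording of Section 5.3 and of the guidance on the adverse event form. No new data and no change to design or sample size are needed. One side effect should be accepted knowingly: events with a pattern or logical link but no time link, which a literal reading now places in *Probable*, would go to *Unknown*.

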6 DIRECT ACCESS TO SOURCE DATA/DOCUMENTS

The investigator(s) must maintain, at all times, the primary records (i.e., source documents) of each patient's data. Examples of source documents are hospital records, office visit records, films, examining physician's finding or notes, consultant's written opinion or notes.

The investigator(s) will maintain a confidential patient identification list that allows the unambiguous identification of each patient. All study-related documents must be kept until notification by 7D Surgical

7 QUALITY CONTROL AND QUALITY ASSURANCE

7.1 Protocol Amendments, Protocol Deviations and Violations

7.1.1 Protocol Amendments

No changes from the final approved protocol will be initiated without prior written approval or favorable opinion of a written amendment by 7D Surgical, except when necessary to eliminate immediate hazards to the patients or when the change involves only logistics or administration.

7.2 Information to Study Personnel

The investigator is responsible for giving information about the study to all staff members involved in the study or in any element of patient management, both before starting the practical performance of the study and during the course of the study (e.g., when new staff become involved). The investigator must ensure that all study staff members are qualified by education, experience, and training to perform their specific responsibilities. The monitor is responsible for explaining the protocol to all study staff, including the investigator, and for ensuring their compliance with the protocol.

8 ETHICS

8.1 Informed Consent

Written informed consent will be obtained from each patient before any study-specific procedures or assessments are done, and after the aims, methods, anticipated benefits, and potential hazards are explained. The patient's willingness to participate in the study will be documented in writing in a consent form, which will be signed by the patient with the date of that signature indicated. The investigator will keep the original consent forms and copies will be given to the patients. It will also be explained to the patients that they are free to refuse entry into the study and free to withdraw from the study at any time without prejudice to future treatment.

Written and/or oral information about the study will be provided in understandable language to all patients.

8.2 Institutional Review Board (IRB)

Before commencement of this study, the protocol will be submitted to the CRP and IRB for evaluation. As required, the study will not start before approval to proceed.

9 REPORTING AND PUBLICATION OF RESULTS

All unpublished information given to the investigator by 7D Surgical shall not be published or disclosed to a third party without the prior written consent of 7D Surgical.

When 7D Surgical generates reports from the data collected in this study for presentation to regulatory authorities, drafts may be circulated to the investigator for comments and suggestions. An endorsement of the final report will be sought from the investigator when required by local regulatory agencies.

All information concerning the MvIGS, 7D Surgical operations, patent application drawings or formulas, manufacturing processes, basic scientific data and design or formulation information, supplied by the sponsor to the investigator and not previously published, is considered confidential and remains the sole property of 7D Surgical. No patent application(s) based on the results of the study may be made by the investigator nor

may assistance be given to any third party to make such an application without the written authorization of 7D Surgical.

The following is a listing of the reports the investigator shall submit to 7D Surgical:

- Adverse event reports as required;
- Progress reports on the clinical study;
- A final report must be provided within 6 months following termination or completion of the investigation or the investigator's part of the investigation.

